# 1 Overview of HVTN 705/VAC89220HPX2008

HVTN 705/VAC89220HPX2008 is a multicenter, randomized, double-blind, placebo-controlled phase 2b efficacy study and plans to enroll 2600 HIV-uninfected women between the age of 18 and 35. The objective of the study is to evaluate the preventive vaccine efficacy (VE) of a heterologous prime/boost regimen utilizing Ad26.Mos4.HIV and aluminum-phosphate adjuvanted Clade C gp140 for the prevention of HIV infection (from confirmed HIV-1 infections diagnosed between the Month 7 and Month 24 visits).

## 2 Objectives and Endpoints

HVTN 705/VAC89220HPX2008 evaluates the preventive VE of a heterologous prime/boost regimen utilizing Ad26.Mos4.HIV and aluminum-phosphate adjuvanted Clade C gp140 for the prevention of HIV infection in HIV-seronegative women residing in sub-Saharan Africa (from confirmed HIV-1 infections diagnosed between the Month 7 and Month 24 visits).

### 2.1 Primary Objectives and Endpoints

*Primary objective 1:*

To evaluate the preventive vaccine efficacy (VE) of a heterologous prime/boost regimen utilizing Ad26.Mos4.HIV and aluminum-phosphate adjuvanted Clade C gp140 for the prevention of HIV infection in HIV-seronegative women residing in sub-Saharan Africa from confirmed HIV-1 infections diagnosed between the Month 7 and Month 24 visits

*Primary endpoint 1:*

Vaccine efficacy as derived from confirmed HIV-1 infections diagnosed between the Month 7 and Month 24 visits

*Primary objective 2:*

To evaluate the safety and tolerability of a heterologous prime/boost regimen utilizing Ad26.Mos4.HIV and aluminum-phosphate adjuvanted Clade C gp140 for the prevention of HIV infection in HIV-seronegative women residing in sub-Saharan Africa

*Primary endpoint 2:*

Local and systemic reactogenicity signs and symptoms for 3 days after each vaccination, adverse events for 30 days after each vaccination, and serious adverse events, AESIs, and adverse events leading to early participant withdrawal or early discontinuation of study product(s) administration for the entire duration of the study

## 2.2 Secondary Objectives and Endpoints

*Secondary objective 1:*

To evaluate vaccine efficacy from enrollment through 24 months

*Secondary endpoint 1:*

HIV-1 infection diagnosed after enrollment through 24 months post enrollment

*Secondary objective 2:*

To evaluate vaccine efficacy from enrollment through 36 months if Stage 2 occurs

*Secondary endpoint 2:*

HIV-1 infection diagnosed after enrollment through 36 months post enrollment

*Secondary objective 3:*

To evaluate vaccine efficacy from month 13 through month 24

*Secondary endpoint 3:*

HIV-1 infection diagnosed after month 13 through 24 months post enrollment

*Secondary objective 4:*

To evaluate vaccine efficacy from month 13 through month 36 if Stage 2 occurs

*Secondary endpoint 4:*

HIV-1 infection diagnosed after month 13 through 36 months post enrollment

*Secondary objective 5:*

To evaluate the immunogenicity of the vaccine regimen

*Secondary endpoint 5:*

Immune responses at the study visits following the third and fourth vaccinations from assays based on the HVTN Laboratory Assay Algorithm such as vaccine-specific binding antibodies and T-cell responses.

*Secondary objective 6:*

To evaluate immunogenicity and immune response biomarkers among vaccine recipients after the third vaccination as correlates of risk of subsequent HIV acquisition and correlates of vaccine efficacy, if deemed applicable.

*Secondary endpoint 6:*

Immune responses from assays based on the HVTN Laboratory Assay Algorithm (available at <https://atlas.ssharp.org/>) and/or more assays down-selected from a larger pool of pilot studies, in HIV-1infected vaccine cases and HIV-1uninfected vaccine controls

*Secondary objective 7:*

To evaluate VE adjusting for various demographic and other baseline characteristics

*Secondary endpoint 7:*

HIV-1 infection diagnosed after the third vaccination by demographic and other baseline characteristics

*Secondary objective 8:*

If significant positive evidence of vaccine efficacy from month 7 through 24 months is seen, to assess if and how vaccine efficacy depends on genotypic characteristics of HIV such as signature mutations

*Secondary endpoint 8:*

HIV-1 infection diagnosed after month 7 through Month 24 and genotypic characteristics of viral sequences from HIV-1-infected participants at HIV-1 diagnosis, such as signature site mutations

*Secondary objective 9:*

To evaluate and compare genomic sequences of viral isolates from HIV-1-infected vaccine and placebo recipients, and use sieve analysis methods to assess whether VE differs by genotypic or phenotypic characteristics of exposing HIVs and whether there is evidence of vaccine-induced immune pressure on the viral sequences

*Secondary endpoint 9:*

Viral sequences from HIV-1-infected participants at the earliest available postinfection timepoint and possible subsequent visits

## 2.3 Exploratory Objectives

*Exploratory objective 1:*

To evaluate vaccine effects (vaccine activity) on virologic and immunologic outcomes (eg, HIV-1 viral load (VL) and postdiagnosis CD4+ T-cell count) among HIV-1-infected participants for 6 months post diagnosis accounting for ARV use

*Exploratory objective 2:*

To explore the association between the vaginal microbiome as well as genital inflammation, and HIV infection risk

*Exploratory objective 3:*

To evaluate early and innate immune responses (eg, whole blood transcriptomics, serum cytokines) one day after the third vaccination (ie, the first protein boost) as correlates of risk of subsequent HIV acquisition

*Exploratory objective 4:*

To evaluate local and systemic reactogenicity signs and symptoms that arise from day 4 to day 7 at a subset of clinical research sites

*Exploratory objective 5:*

To further evaluate the immunogenicity of the vaccine regimen, additional immunogenicity assays may be performed, and assays may be performed on samples from other timepoints, based on the HVTN Laboratory Assay Algorithm

*Exploratory objective 6:*

To assess use of biomedical interventions and biological and behavioral factors in the study

cohort and how they modify vaccine efficacy

*Exploratory objective 7:*

To evaluate the role of host genetic factors in the immune response to the vaccine regimen and in vaccine effects on study endpoints

*Exploratory objective 8:*

To perform comparative analyses of correlates of risk identified in HVTN 705 and those identified in other HIV vaccine efficacy studies

*Exploratory objective 9:*

To conduct analyses related to furthering the understanding of HIV, immunology, vaccines, and clinical trial conduct

### 3 Follow-Up Period

All participants will be followed for at least 24 months post-enrollment. Participants will receive vaccinations at Months 0, 3, 6, and 12 and be followed for HIV infection for a period of at least 2 years (stage 1) after enrollment until the primary analysis at the end of stage 1 is performed (when the last subject reaches the month 24 visit). Participants who become HIV-1 infected during the study will be followed for approximately 6 months after confirmation of diagnosis.

### 4 Study Populations

The following study populations or analysis sets are used for addressing the study objectives.

- **Full Analysis Set (FAS):** all randomized participants who receive at least 1 vaccine administration
- **Modified Intent-to-Treat (MITT) Population:** participants in the FAS who are HIV-1 uninfected on the date of first vaccination.
- **Per-Protocol (PP) Population:** participants in the FAS who are HIV-1 uninfected 4 weeks after the 3rd vaccination visit, who received all planned vaccinations at the first 3 vaccination visits within the respective visit windows and have no other major protocol deviations that were judged to possibly impact the efficacy of the vaccine.
- **Full Immunization Set (FIS):** participants in the FAS who are HIV-1 uninfected 4 weeks after the 4th vaccination visit and who receive all planned vaccinations within the respective visit windows.

- **At risk Immunogenicity Cohort (IC-at risk):** participants in the FAS who are selected for measurement of immune response endpoints at the primary immunogenicity timepoints and who are HIV-1 uninfected 4 weeks after the 3rd vaccination visit, who have no other major protocol deviations that were judged to possibly impact the efficacy of the vaccine.
- **Per Protocol Immunogenicity Cohort (IC-PP):** participants in the IC-at risk who received all planned vaccinations at the first 3 vaccination visits within the respective visit windows.

The MITT population and the FAS are very similar but not identical to a full Intention-to-Treat Cohort (ie, all randomized participants); the FAS differs by excluding randomized volunteers who do not enroll (ie, dont receive any vaccinations); and the MITT population is the subset of the FAS that also excludes randomized participants discovered later to be HIV-1 positive by day 0. Because of blinding and the brief length of time between randomization and enrollment (typically no more than 4 working days) we expect almost all randomized volunteers to be in the FAS. Given that eligibility for the study requires recent evidence of being HIV-1 uninfected (within 45 days prior to enrollment), we expect almost all enrolled participants to also be in the MITT Cohort.

The analyses of safety will be performed on the FAS. The primary analysis of vaccine efficacy will be based on the PP population. Secondary analyses of vaccine efficacy will be based on the MITT population and the FIS. Analyses of vaccine immunogenicity and immune correlates of risk will be based on IC-at risk, IC-PP and the FIS (for those with immunogenicity outcomes).

In addition, 4 cohorts of participants who are diagnosed with HIV-1 infection during the trial are analyzed for addressing various study objectives. Terminology for these cohorts is defined in Table 1, which will be used throughout the SAP.

Since this is a proof-of-concept trial, all efficacy analyses will be done according to the as treated principle (ie, actually received treatments), except for analyses using the MITT population.

In the unexpected event of a duplicate enrollment, the interim safety data will be reported for each enrollment, considering these as separate participants, while noting in the report that a duplicate enrollment occurred. All final analyses will only include unique participants. For duplicate enrollments, the data collected under each enrollment will be combined and the participant will be identified using the participant ID of the first enrollment. For ‘as treated’ analyses, the treatments received across both enrollments will be considered when determining the treatment group. MITT analyses will use the treatment group assigned at randomization from the first enrollment. These doubly-enrolled participants are excluded from the PP cohort.

Table 1: Cohorts of HIV-1 infected study participants.

Cohort Name	Definition of Cohort
MITT infected by 24 Months cohort	Participants in the MITT population who are diagnosed with HIV-1 infection during the follow-up period after enrollment through the Month 24 visit
MITT infected by 36 Months cohort	Participants in the MITT population who are diagnosed with HIV-1 infection during the follow-up period after enrollment through the Month 36 visit
Per-Protocol infected by 24 Months cohort	Participants in the PP population who are diagnosed with HIV-1 infection during the follow-up period on or after the Month 7 visit through the Month 24 visit
Per-Protocol infected by 36 Months cohort	Participants in the PP population who are diagnosed with HIV-1 infection during the follow-up period on or after the Month 7 visit through the Month 36 visit

## 5 Definition of the Primary Efficacy Endpoint (Documented HIV-1 Infection)

### 5.1 HIV Testing Postvaccination

The vaccine efficacy endpoint is diagnosis of HIV-1 infection during the follow-up period. Following enrollment, HIV testing will take place at scheduled clinic visits defined in Appendix E and Appendix G of the CTP.

In-study HIV testing will be performed according to the HVTN HIV diagnostic testing algorithms. Routinely, specimens are initially assayed with an HVTN Lab Program approved HIV 1/2 enzyme immunoassay (EIA) or chemiluminescent microparticle immunoassay (CMIA). If the EIA/CMIA is reactive, nucleic acid polymerase chain reaction (PCR) test to detect HIV-1 RNA will be performed as indicated in the algorithm. The algorithm is repeated on a second specimen to confirm a diagnosis of HIV-1 infection. The second specimen for confirmatory testing may be collected at an interim visit (designated as visit #.X, where # is the visit at which the first reactive test was obtained and X designates the interim visit; specified in Appendix F and Appendix H of the CTP). Samples to be stored for future immunogenicity or virology studies will also be collected at this time (Appendix F of the CTP).

A case will be defined as a participant with confirmed detectable HIV-1 nucleic acid PCR on

2 different specimen collection dates. The nucleic acid test will most commonly be the HIV-1 RNA PCR viral load test. Confirmation of HIV-1 infection will be determined as dictated by the HVTN HIV testing algorithm (available on the HVTN 705 protocol-specific website). Before issuing an HIV-1 infection report for a participant diagnosed with HIV-1 infection prior to study unblinding, all testing results will be reviewed by a blinded, independent Endpoint Adjudicator(s) and/or designee(s).

If a participant is confirmed to have become HIV-1 infected prior to study unblinding, plasma HIV-1 viral RNA will be measured on archived samples collected according to Appendix E. In addition to plasma HIV-1 viral RNA testing, participants may also have measurements of immunogenicity assessments and a clinical assessment performed at all postinfection visits (see Appendix F of the CTP).

## 5.2 Endpoint Adjudication

The diagnostic criteria for HIV-1 infection outside the setting of a vaccine trial are well accepted. However, definitive diagnosis of HIV-1 infection in the context of having received an HIV vaccine that is even partially effective may be more difficult. Specifically, if the immune responses elicited by vaccination are capable of completely suppressing viral replication, or if vaccination alters the normal serological response upon exposure to HIV-1, standard diagnostic tests may be more difficult to assess. Therefore, the HVTN will have an endpoint adjudication process to assess all serological and virological testing, in a blinded manner, on each participant in the trial who, prior to study unblinding, tests positive per the HVTN 705 HIV-1 diagnostic testing algorithm. The assessment of the Endpoint Adjudicator(s) or designee(s) will be reported to the SDMC and to the HIV diagnostics laboratory.

The Endpoint Adjudicator(s) and/or designee(s) must notify the SDMC within 1 working day of any confirmed HIV-1 infection. The HIV diagnostics lab will inform the clinic of the outcome of the HIV testing algorithm (ie, HIV infected, HIV uninfected, or redraw required).

The Endpoint Adjudicator(s) and/or designee(s) will be an expert in the fields of infectious diseases or laboratory medicine independent of the clinical investigators participating in this trial.

## 5.3 Date of HIV-1 Infection for vaccine efficacy

The primary analysis will be done in the PP population where participants becoming HIV infected or dropping out before the visit (4 weeks post vaccination 3 visit) after the third vaccination or not having received all of the first 3 vaccinations within the specified time window or having a major specified protocol deviation, will be excluded from the analysis. The date of HIV-1 diagnosis will be the draw date of the first sample that leads to a positive test result by the diagnostic algorithm described above. Dropouts will be censored at the

time of their last HIV-1 negative test.

## 6 Interactions of Study Statisticians with the Data and Safety Monitoring Board

At each 6-monthly Data and Safety Monitoring Board (DSMB) meeting, the study statisticians will present Open, Chair/Medical Officer, and Closed Reports; all tables and figures included in the Closed Report are specified in Appendix A with statistical analyses of safety further described in Section 7. For a subset of tables and figures in the Closed report, the Open Report includes tables and figures with the same information except with trial information presented pooled across the two treatment groups to preserve blinding to treatment assignment. In addition, the following interim monitoring reports will be presented at each DSMB meeting:

- monitoring report of vaccine efficacy for potential harm, non-efficacy, and high efficacy per Section 10.1, where
  - potential harm monitoring starts at the 10th pooled MITT infection endpoint and is continually performed with each additional endpoint until the time non-efficacy/high efficacy monitoring is triggered,
  - non-efficacy monitoring starts at the 60th pooled MITT infection and proceeds at every scheduled DSMB meeting thereafter (anticipated every six months) until the end of Stage 1, and
  - high efficacy monitoring is harmonized with non-efficacy monitoring and starts when 150 MITT participants reach their Month 36 visit (end of Stage 2); if Stage 2 occurs, one additional high efficacy interim analysis will be performed at 6 months after the end of Stage 1;
- monitoring of the use of Truvada as pre-exposure prophylaxis (PrEP) first reported for the April 2019 DSMB meeting per Section 10.2;
- monitoring report for futility to assess vaccine efficacy per Section 10.3 starting at the latest 12 months after the first participant is enrolled and continuing every 6 months thereafter; and
- monitoring report for performance standards of quality of trial conduct per Section 10.4.

## 7 Statistical Analysis of Safety

The analyses of safety will be performed on the FAS, all randomized participants who receive at least 1 vaccine administration. All safety analyses will be tabulated by treatment group

(active vaccine, placebo) according to the as-treated principle.

## **7.1 Baseline Comparability**

Treatment groups will be compared for baseline characteristics including demographics and laboratory measurements, using descriptive statistics (percentages, means, ranges).

### **7.1.1 Reactogenicity**

The number and percentage of participants experiencing each type of reactogenicity sign or symptom will be tabulated by severity, treatment group and the length of reactogenicity follow-up (3 days versus 7 days) and the percentages will be displayed graphically by arm and the length of reactogenicity follow-up (3 days versus 7 days). For a given sign or symptom, each participants reactogenicity will be counted once under the maximum severity for each injection visit. In addition, to the individual types of events, the maximum severity of local pain or tenderness, induration or erythema, and of systemic symptoms will be calculated. Kruskal-Wallis tests will be used to test for differences in severity between arms.

### **7.1.2 AEs and SAEs**

AEs occurring during the first 30 days after vaccination will be summarized using MedDRA System Organ Class and preferred terms. SAEs will be shown for the whole study period. Tables will show by treatment group the number and percentage of participants experiencing an AE within a System Organ Class or within preferred term category by severity and by relationship to study product. For the calculations in these tables, a participant with multiple AEs within a category will be counted once under the maximum severity and by causal relationship to study product. Formal statistical testing comparing arms is not planned since interpretation of differences must rely heavily upon clinical judgment. Parallel analyses will include all AEs and AEs leading to participant withdrawal or early discontinuation of study product(s). A listing of SAEs reported to the Janssen Global Medical Safety Group will provide details of the events including severity, relationship to study product, time between onset and last vaccination, and number of vaccinations received.

### **7.1.3 Reasons for vaccination discontinuation and early study termination**

The number and percentage of participants who discontinue vaccination and who terminate the study early will be tabulated by treatment arm and including the reason for discontinuation.

## 8 Statistical Analysis of Vaccine Efficacy

Except where specified, all vaccine efficacy endpoint analyses are performed in the PP cohort. All analyses only use samples and data collected prior to study unblinding. The final vaccine efficacy analysis will occur when the last enrolled participant has reached the month 36 visit.

### 8.1 Primary Analysis of Vaccine Efficacy

The time between enrollment and the date of HIV-1 infection diagnosis determined in Section 5 is evaluated for all subjects. Subjects becoming HIV-infected or dropping out before their month 7 visit or not having received all of the first 3 vaccinations within the specified time window or having a major protocol deviation will be excluded from the primary PP analysis. **The failure times of participants with last HIV-negative test at or after the month 24 visit are right-censored at the right edge of the month 24 allowable visit window [defined as 60 days after the target day (728 days) for the month 24 visit, equal to 25.91 months post-enrollment]. For participants with last HIV-negative test prior to the month 24 visit and without diagnosis of the HIV-1 infection primary endpoint at or before the month 24 visit, their failure times are right-censored at the date of the last HIV-negative test.**

We define the primary vaccine efficacy parameter,  $VE(7-24)$ , as one minus the probability of the primary efficacy endpoint between the month 7 and month 24 visit for the vaccine group divided by the probability of the primary efficacy endpoint between the month 7 and month 24 visit for the placebo group times 100 percent. **More specifically, the primary VE parameter,  $VE_{7-24}(\tau)$ , will be estimated at the fixed time point  $\tau = 25.91$  months post-enrollment with the specification of the value of  $\tau$  determined as noted above.** Each of the two cumulative incidence parameters in  $VE_{7-24}(\tau)$  will be estimated using the transformed Nelson-Aalen estimator for the cumulative hazard function evaluated at time  $\tau$  defined above. We will use the delta method to obtain the asymptotic 95% CI for the log cumulative incidence ratio (vaccine/control) and then back-transform these confidence bounds to the VE scale. Both the point estimate and the 95% CI for VE will be reported.

$VE(\tau)$  is the target parameter for the primary analysis of overall VE. The primary analysis tests

$$\begin{aligned} &\text{the null hypothesis } H_0: VE_{7-24}(\tau) = 0\% \text{ versus} \\ &\text{the alternative hypothesis } H_1: VE_{7-24}(\tau) \neq 0\% \end{aligned} \tag{1}$$

using a 2-sided  $\alpha = 0.05$  level Wald test of the equality of log cumulative hazard functions at  $\tau$  for the vaccine group and the control group.

Cox proportional hazards model will also be used for estimating  $VE(7-24)$ , measured by 1 minus the hazard ratio (vaccine vs. placebo) and for a score test of whether the  $VE(7-24)$  differs from 0%.

As a sensitivity analysis to the primary analysis of vaccine efficacy in the PP population, targeted minimum loss-based estimation (TMLE) is used to estimate this vaccine efficacy parameter. TMLE is used to estimate the cumulative incidences of HIV-1 infection over time for each of the vaccine and placebo groups, through to Month 24. These estimates will then be contrasted to estimate the primary VE parameter  $VE(7-24)$ , which adjusts for covariates. This analysis can correct for bias due to measured participant covariates that predict both per-protocol status and HIV-1 infection. As part of the implementation of the TMLE the Super Learner is used to generate initial estimates of the conditional censoring distribution and the iterated conditional means.

In addition, to assess potential time-effects of vaccine efficacy, the Kaplan-Meier method will be used to plot the estimated cumulative incidence rates over time for the vaccine and placebo groups. This method will be used to estimate (i) cumulative vaccine efficacy over time, defined as  $(1 \text{ minus the ratio (vaccine/placebo) of cumulative incidence by time } t) \times 100\%$ , and (ii) additive-difference vaccine efficacy over time, defined as the difference (placebo minus vaccine) in cumulative incidence by time  $t$ , with the method of [Parzen, Wei, and Ying \(1997\)](#) applied to obtain pointwise and simultaneous 95% CIs. In addition, the longitudinal targeted minimum loss-based estimation method as implemented in the R package `survtmle` will be used for estimation, which in addition to allowing confounding adjustment can correct for potential bias due to covariate-dependent censoring.

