6.4 Accrual and sample size

6.4.1 Sample size calculation for proof of concept endpoints (vaccine efficacy of a prime-boost regimen to prevent HIV-1 infection)

A targeted total of 2,600 HIV-uninfected adult women will be recruited. Trial participants will be enrolled over a 14-month period approximately and randomized to a placebo or vaccine regimen (1:1 randomization). Participants will receive vaccinations at Months 0, 3, 6, and 12 and be followed for HIV infection for a period of at least 2 years (stage 1) after enrollment until the primary analysis at the end of stage 1 is performed (when the last subject reaches the month 24 visit). If H0: $VE(7-24) \le 0\%$ is rejected at the end of Stage 1, then the trial participants will continue blinded follow-up for at least 36 months (stage 2). If stage 2 does not occur, then all trial participants will be unblinded at the end of stage 1.

The trial is designed so that a 0.025-level Wald test has approximately 90% power in the PP population to reject the null hypothesis:

H0: $VE(7-24) \le 0\%$ versus the alternative hypothesis H1: VE(7-24) > 0% if the level of VE(7-24) is 50%.

The sample size calculations are based on the power of a 1-sided 0.025-level Wald test for comparing cumulative incidences of HIV-1 infection by the Month 24 visit between randomized groups, in the presence of the sequential monitoring described below. Power is computed by simulating a large number of efficacy trials under assumptions described below using the R package seqDesign [46,47],

The following assumptions are made for the sample size calculations:

- 10% annual dropout incidence in each of the study groups
- halved VE in the first 7 months after enrollment
- 14-month uniform accrual with halved accrual during the first 3 months
- visits approximately every 3months for HIV-1 diagnostic tests
- 4.2% annual HIV-1 incidence that is constant over time in the placebo group
- Sequential monitoring of vaccine efficacy for the following outcomes:
 - Potential harm [Conclude that VE(0-24)< 0% based on the one-sided exact binomial test of the proportion of infections assigned to the vaccine group]
 - Non-efficacy [Conclude that VE(7-24) < 40% based on a 2-sided 95% nominal confidence interval for VE(7-24) lying completely below 40%, and VE(0-24) < 40% based on a 2-sided 95% nominal confidence interval for VE(0-24) lying completely below 40%]

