6.7 Randomization of treatment assignments

The randomization sequence will be obtained by computer-generated random numbers through an Interactive Web Response System (IWRS) under provision by the sponsor and provided to each HVTN CRS. The randomization will be stratified by HVTN CRS and done in blocks to ensure balance across arms. At each institution, the pharmacist with primary responsibility for dispensing study products is charged with maintaining security of the treatment assignments. Participants and site staff will be blinded as to the treatment group assignment throughout both Stage 1 and Stage 2, if it occurs.

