### 8.2.2 Vaccine Efficacy Estimates that Adjusts for Covariates

As a supportive analysis of the hypotheses in (1), a doubly robust estimator will be used to estimate cumulative incidences of the primary efficacy endpoint over time in the per protocol population, accounting for both per-protocol and right censoring status. The estimator used for this analysis is described in Westling et al. (2021). Super Learner (van der Laan, Polley, and Hubbard, 2007; Westling, Luedtke, Gilbert, and Carone, 2021) is used to generate initial estimates of the conditional protocol violation and censoring distribution and the iterated conditional means. The Super Learner library is specified in Table 2. If any of the algorithms included in the Super Learner library return an error when run on the trial data (e.g., due to the rarity of the event), then they will be removed. Each method considers adjustment for vaccine/placebo assignment, baseline demographic covariates, and the baseline behavioral risk score built via supervised learning as described in Section 8.5. The particular demographic covariates considered are: site, country, and age at enrollment.

VE parameters will be estimated by 1 minus the ratio (vaccine group/placebo group) of the estimates of the HIV incidence probability between months 7 and 24. Influence-curve based variance estimators of each cumulative incidence are used, and the delta method is applied to obtain the variance estimator of the log cumulative incidence ratio. Point estimates and 95% pointwise and simultaneous Wald CIs for cumulative incidence curves and  $VE(t)$  curves will be plotted. For the final time point of 24 months, 2-sided Wald p-values will be reported.

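### Randomization is stratified by site, but the Cox model and score test (PP and MITT) are specified without site; stratifying them is a cheap, low-priority improvement

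*SAP*

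**What the plan says.** **Randomization.** Protocol 6.7: "The randomization will be stratified by HVTN CRS and done in blocks to ensure balance across arms". The block size is not stated.

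**Primary test.** SAP 8.1 contrasts two arms by transformed Nelson-Aalen estimates, using a 2-sided 0.05 "level Wald test of the equality of log cumulative hazard functions at" τ. No strata or covariates are named.

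**Cox model.** SAP 8.1 adds that a "Cox proportional hazards model will also be used for estimating" VE(7-24) as one minus the vaccine-to-placebo hazard ratio, "and for a score test of whether the" VE differs from zero. Site is not mentioned, and no reason is given. SAP 8.2.1 has the same two tests for the MITT VE(0-24).

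**Where site does appear.** SAP 8.2.2 sets out a doubly robust supportive analysis of the primary hypotheses in the per-protocol (PP) population: "The particular demographic covariates considered are: site, country, and age at enrollment". Site and country are also inputs to the behavioral risk score (SAP 8.5, Table 3). The TMLE sensitivity analysis in SAP 8.1 adjusts for covariates, which protocol 6.9.5.1 describes as baseline demographics plus that risk score.

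**Power.** Protocol 6.4.1 bases power on a "1-sided 0.025-level Wald test for comparing cumulative incidences of HIV-1 infection by the Month 24 visit" and aims for "approximately 90% power in the PP population to reject the null hypothesis" when VE(7-24) is 50%. No site effect is among the listed assumptions.

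**The concern.** When treatment is balanced within sites by design, an analysis that ignores site leaves between-site variation in the error term. The plan itself treats site and country as possible predictors of risk, since both feed the risk score and the adjusted analysis. The Cox model and score test could be stratified by the randomization factor with no new data. As the text stands, a programmer cannot tell whether strata were intended.

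The coverage is also uneven. The site-adjusted analysis in SAP 8.2.2 is tied to the PP hypotheses, and SAP 8.2.1 gives the key secondary MITT analysis no counterpart. The list of end-of-Stage-1 analyses in SAP 9 contains nothing adjusted for site.

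At stake is a small amount of precision and a match between design and analysis. The validity of the primary result is not at stake.

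**Working it through.** **Inputs from protocol 6.4.1 and Table 6-2:** 1300 per arm; placebo incidence 4.2% a year; VE 50% after Month 7 and 25% before; dropout 10% a year; 5% excluded from PP; 1-sided 0.025. **Not in the documents, so assumed:** 10, 20 or 30 sites; log-normal site incidence with CV 0 to 0.8; blocks of 4.

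**1. Reproduce the stated power without any site term** (1300 × 0.95 = 1235 per arm).
- Placebo at risk at Month 7: 1235 × exp(−0.142 × 7/12) = 1136.8. Risk in Months 7 to 24: (0.042/0.142) × [1 − exp(−0.142 × 17/12)] = 0.0539. Events: 61.3.
- Vaccine at risk at Month 7: 1235 × exp(−0.1315 × 7/12) = 1143.8. Risk: (0.021/0.121) × [1 − exp(−0.121 × 17/12)] = 0.0273. Events: 31.3.
- SE = √(1/61.27 + 1/31.27) = 0.2198. Power = Φ(0.6931/0.2198 − 1.96) = 88.4%. Table 6-2 states 87.56%. The same formula gives 77.8% at 3.1% incidence (stated 79.70%) and 94.8% at 5.5% (stated 93.26%).

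So the design power does not depend on site adjustment.

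**2. Approximate ceiling on the gain for a Wald test.** The between-site share of the variance of a binary outcome with mean risk p is CV² × p/(1 − p). The event-weighted mean risk is (61.27 × 0.0539 + 31.27 × 0.0273)/92.54 = 0.0449, so p/(1 − p) = 0.0470. Removing that whole share from SE² gives:

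| CV | Between-site share | Power (88.4% without site) |
|---|---|---|
| 0.2 | 0.2% | 88.4% |
| 0.3 | 0.4% | 88.5% |
| 0.5 | 1.2% | 88.7% |
| 0.8 | 3.0% | 89.3% |

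**3. Simulated Cox score test, VE 50%, 2,500 trials per setting.** The information gain is read as (mean stratified z / mean unstratified z)² − 1.

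| Sites | CV | Mean z, unstratified / stratified | Gain | Power, unstratified → stratified |
|---|---|---|---|---|
| 20 | 0.3 | −3.209 / −3.214 | 0.3% | 90.3% → 90.4% |
| 30 | 0.3 | −3.211 / −3.214 | 0.2% | 90.4% → 90.1% |
| 20 | 0.5 | −3.159 / −3.176 | 1.1% | 89.6% → 89.7% |
| 30 | 0.5 | −3.214 / −3.230 | 1.0% | 90.6% → 90.9% |
| 10 | 0.8 | −3.127 / −3.166 | 2.5% | 88.2% → 88.8% |
| 20 | 0.8 | −3.118 / −3.165 | 3.0% | 89.0% → 89.7% |
| 30 | 0.8 | −3.097 / −3.142 | 2.9% | 88.6% → 88.9% |

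Over all settings the power change ran from −0.3 to +0.7 points, with a Monte Carlo SE of 0.1 to 0.3. A second simulation with 15 to 30 sites gave 1.2 to 1.3% more information at CV 0.5, 3.2 to 3.4% at CV 0.8, and power changes of −0.3 to +0.8 points.

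**4. Homogeneous sites (CV 0).** Score information falls from 23.19 to 23.15 with 20 sites (0.2%) and from 23.16 to 23.09 with 30 (0.3%).

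**5. Type I error under VE = 0, nominal 2.5% one-sided.** Wald 1.8 to 3.0%; unstratified score 2.2 to 2.7%; stratified score 2.1 to 2.8%. The Monte Carlo SE is √(0.025 × 0.975/2500) = 0.3 points.

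**The case against.** The strongest reply is that nothing here is broken and site is already handled. Much of that stands.

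- **Validity.** A reader might infer that the unstratified variance is incorrect. The rejection rates in step 5 do not show that.
- **Cost.** A reader might infer that stratifying is free. With homogeneous sites it loses a trace of information. With about 92 PP events over 10 to 30 sites there are only about 3 to 9 events per site, so a pooling rule is needed.
- **Hazard-ratio attenuation.** A reader might count this as an error in the primary analysis. The primary parameter is a marginal cumulative-incidence ratio, so it is not one. It is also tiny. With gamma-distributed site incidence (an assumption) and a two-year placebo cumulative hazard of 0.084, the marginal VE is 1 − ln(1 + CV² × 0.042)/ln(1 + CV² × 0.084), which is 49.9% at CV 0.3 and 49.2% at CV 0.9 for a true 50%.
- **Existing coverage.** Site is used in SAP 8.2.2, in the risk score and, through that score, in the TMLE.

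The coverage argument has limits. SAP 8.2.2 concerns the PP hypotheses only. Several candidates in its learner library (Table 2) omit the demographic covariates, so direct use of site is data-driven. Protocol 6.9.5.2 says in general terms that the primary-type analyses, TMLE included, are repeated for MITT, but the SAP does not carry that into a named site-adjusted MITT analysis.

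**Conclusion.** The mismatch is real: randomization is stratified by CRS, and the Cox model and score test for PP and MITT are specified without it. The gain from stratifying is small and depends on how far incidence differs between sites: about 0 to 3% of information and under 1 point of power for CV up to 0.8, against a loss of about 0.1 to 0.3% of information if sites do not differ.

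These figures rest on assumed site numbers, site CV and block size, on continuous infection times rather than three-monthly visits, and on no interim stopping.

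A reader might go further and ask for the primary Wald test to be replaced. The documents do not support that. The test is valid, it is the basis of the power calculation, and SAP 10.1.2 uses the same method for interim non-efficacy monitoring. The SAP's modification history also records that the final analysis was implemented on May 2, 2022, so a replacement now would be a change made after results.

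This is a cheap improvement of low priority.

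**What to change.** 1. Keep the unstratified Nelson-Aalen Wald test as the primary analysis.
2. In SAP 8.1 and 8.2.1, state that the Cox model and score test are stratified by CRS. Give the pooling rule in advance, for example that sites with fewer than a fixed number of events, counted over both arms, are merged within country.
3. Extend the site-adjusted cumulative-incidence estimator of SAP 8.2.2 to the MITT VE(0-24).
4. Report these beside the primary and key secondary results, labelled as added after the final analysis.

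The cost is a few sentences of SAP text, one stratification term in the Cox code and one further run of an estimator already planned. No new data are needed. There are two downsides: the trace loss of information if sites are alike, and a stratified hazard ratio that is conditional on site rather than marginal, which should be said where it is reported.
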